## **11. APPENDIX A: TABLE SHELLS**

## Appendix A: Table shells

Table 1: Study population and subgroups for main analysis

	Exposed	Unexposed	Total
Pregnant women eligible per inclusion/exclusion criteria, n			
With pregnancy outcome, n (%)			
With unknown pregnancy outcome, n (%)			
Lost to follow up, n (%)			
Pregnant women with multiple gestation, n (%)			
Pregnant women with KPSC delivery, n (%)			
Pregnant women with index date prior to 37 weeks gestation, n (%)			
With live birth, n (%)			
KPSC live born infants, n			
Singleton only, n (%)			

## Appendix A: Table shells

Table 2. Baseline characteristicsa of Boostrix exposed and unexposed pregnant women

	Exposed N =	Unexposed N =	Total N =	p value
Maternal age at pregnancy start				N/A d
mean (sd)				
median				
Q1, Q3				
range				
Race/ethnicity, n (%)				N/A
White				
Black				
Hispanic				
Asian				
Other				
Gestational age in weeks at index				N/A
27-30				
31-36				
≥37				
Current smoker, n (%)				
Yes				
No				
Alcohol use, n (%)				
Yes				
No				
Continuous membership, n (%)				
Yes				
No				
Medicaid insurance, n (%)				
Yes				
No				
Any hospitalization or ED visit, n (%)				
Yes				
No				
Number of outpatient visits, n (%)				
0-4				
5-12				
≥13				
Number of previous pregnancies, n (%)				
0				
1				
≥2				
Missing				
History of pregnancy loss, n (%)				
Yes				
No				
Season of pregnancy start, n (%)				
September-March				
April-August				
Received other vaccines b , n (%)				
Yes				
No				
Received vaccines containing diphtheria, tetanus toxoid, or pertussis antigens within one year before pregnancy, n (%)				
Yes				
No				
High-risk medical condition, n (%)	Multiple gestation			N/A
Thyroiditis				
Diabetes				
Other autoimmune diseases				
Renal diseases				
Cardiac diseases				
Pre-pregnancy obesity c				
Missing				
Pre-existing hypertension				
Rhesus sensitization				
HIV infection				
Syphilis infection				
Cervical incompetence				

a Baseline characteristics were defined from pregnancy start to index date, unless otherwise specified

b Other vaccines included: inactivated influenza vaccine (xx%), hepatitis A/hepatitis B vaccine (xx%), human papillomavirus vaccine (xx%), and other (xx%).

c BMI>40 within 6 months prior to pregnancy start

d N/A= not applicable, for matching variable

Appendix A: Table shells

Table 3. Characteristics of KPSC live born infants with Boostrix exposed and unexposed mothers

	Exposed N =	Unexpose N =
Sex, n (%)		
F		
M		
Gestational age in weeks at birth, n (%)		
27-33		
34-36		
37-39		
≥40		
Birth weight, g		
mean (sd)		
median		
Q1, Q3		
range		
Missing		
Birth length, cm		
mean (sd)		
median		
Q1, Q3		
range		
Missing		
Head circumference, cm		
mean (sd)		
median		
Q1, Q3		
range		
Missing		
Apgar 1 score, n (%)		
≤3		
4-6		
≥7		
Missing		
Apgar 5 score, n (%)		
≤3		
4-6		
≥7		
Missing		

## Appendix A: Table shells

Table 4. Incidence and relative risk of primary endpoints comparing Boostrix exposed and unexposed cohorts

	Exposed				Unexposed				Relative Risk e ( Wald 98.75% CI)	
	Number of Persons	Number of Person years	Number of adverse events	Incidence per 1000 persons or person-years (95% CI)	Number of Persons	Number of Person years	Number of adverse events	Incidence per 1000 persons or person-years (95% CI)	Unadjusted	Adjusted
Pre-eclampsia and eclampsia a										
Intra-uterine infections a										
Small for gestational age b			N/A*				N/A			
Preterm delivery c			N/A				N/A			

a Identified among all pregnant women eligible for main analysis

b Identified among KPSC live born infants, singleton only

c Identified among pregnant women with live birth, with index (vaccination) date prior to 37 weeks gestation

d Adjusted for covariates XXX (place holder, covariates may differ for each endpoint)

e Poisson regression model with robust variance estimate

\* N/A=Not Applicable

Table 5. Incidence and relative risk of secondary endpoints comparing Boostrix exposed and unexposed cohorts

	Exposed				Unexposed				Relative Risk ( Wald 95% CI)	
	Number of Persons	Number of Person years	Number of events	Incidence per 1000 persons or person-years (95% CI)	Number of Persons	Number of Person years	Number of events	Incidence per 1000 persons or person-years (95% CI)	Unadjusted	Adjusted
Poor fetal growth, IUGR a										
Placental abruption a										
Preterm pre-labor rupture of membranes (PPROM) b										
Maternal death a										
Stillbirth/fetal death c			N/A*			N/A				
With congenital anomalies			N/A			N/A			N/A	N/A
Post-partum hemorrhage d			N/A			N/A				
Neonatal death e			N/A			N/A				
Congenital anomalies at birth and through 6 months of age d			N/A			N/A			N/A	N/A
Congenital anomalies of nervous system			N/A			N/A				
Congenital anomalies of eye			N/A			N/A				
Congenital anomalies of ear, face, or neck			N/A			N/A				
Congenital anomalies of cardiovascular system			N/A			N/A				
Congenital anomalies of respiratory system			N/A			N/A				
Clefts			N/A			N/A				
Congenital anomalies of upper gastrointestinal system			N/A			N/A				
Congenital anomalies of lower gastrointestinal system			N/A			N/A				
Congenital anomalies of genital organs			N/A			N/A				
Congenital anomalies of renal system			N/A			N/A				
Congenital anomalies of musculoskeletal system			N/A			N/A				
Congenital anomalies of limb			N/A			N/A				
Congenital anomalies of integument			N/A			N/A				
Other and unspecified congenital anomalies			N/A			N/A				
Number of congenital anomalies (based on body system) per infant			N/A		N/A		N/A		N/A	N/A
0			N/A		N/A		N/A		N/A	N/A
1			N/A		N/A		N/A		N/A	N/A
2			N/A		N/A		N/A		N/A	N/A
3			N/A		N/A		N/A		N/A	N/A
≥4			N/A		N/A		N/A		N/A	N/A

a Identified among all pregnant women eligible for main analysis

b Identified among pregnant women with index (vaccination) date prior to 37 weeks gestation

c Identified among pregnant women with pregnancy outcome

d Identified among pregnant women with KPSC delivery

e Identified among KPSC live born infants

f Adjusted for covariates XXX (place holder, covariates may differ for each endpoint)

g Poisson regression model with robust variance estimate (place holder)

\* N/A=Not Applicable

Appendix A: Table shells

Table 6: Study population and subgroups for descriptive analysis

	Exposed
Pregnant women eligible per inclusion/exclusion criteria, n	
With pregnancy outcome, n (%)	
With unknown pregnancy outcome, n (%)	
Lost to follow up, n (%)	
Pregnant women with multiple gestation, n (%)	
Pregnant women with KPSC delivery, n (%)	
Pregnant women with index date prior to 37 weeks gestation, n (%)	
With live birth, n (%)	
KPSC live born infants, n	
Singleton only, n (%)	

## Appendix A: Table shells

Table 7. Baseline characteristicsa of pregnant women vaccinated with Boostrix before the 27th week of gestation

	Exposed	N =
Maternal age at pregnancy start, years		
	mean (sd)	
	median	
	Q1, Q3	
	range	
Race/ethnicity, n (%)		
White		
Black		
Hispanic		
Asian		
Other		
Gestational age in weeks at index date, n (%)		
27-30		
31-36		
≥37		
Current smoker, n (%)		
Yes		
No		
Alcohol use, n (%)		
Yes		
No		
Continuous membership, n (%)		
Yes		
No		
Medicaid insurance, n (%)		
Yes		
No		
Any hospitalization or ED visit, n (%)		
Yes		
No		
Number of outpatient visits, n (%)		
0-4		
5-12		
≥13		
Number of previous pregnancies, n (%)		
0		
1		
≥2		
Missing		
History of pregnancy loss, n (%)		
Yes		
No		
Season of pregnancy start, n (%)		
September-March		
April-August		
Received other vaccines b , n (%)		
Yes		
No		
Received vaccines containing diphtheria, tetanus toxoid, or pertussis antigens within one year before pregnancy, n (%)		
Yes		
No		
High-risk medical condition, n (%)		
Multiple gestation		
Thyroiditis		
Diabetes		
Other autoimmune diseases		
Renal diseases		
Cardiac diseases		
Pre-pregnancy obesity c		
Missing		
Pre-existing hypertension		
Rhesus sensitization		
HIV infection		
Syphilis infection		
Cervical incompetence		

a Baseline characteristics were defined from pregnancy start to index (vaccination) date, unless otherwise specified

b Other vaccines included: inactivated influenza vaccine (xx%), hepatitis A/hepatitis B vaccine (xx%), human papillomavirus vaccine (xx%), and other (xx%).

c BMI>40 within 6 months prior to pregnancy start

## Appendix A: Table shells

Table 8. Characteristics of KPSC live born infants with mothers vaccinated with Boostrix before the 27th week of gestation

	Exposed
	N =
Sex, n (%)	
F	
M	
Gestational age in weeks at birth, n (%)	
27-33	
34-36	
37-39	
≥40	
Birth weight, g	mean (sd)
	median
	Q1, Q3
	range
	Missing
Birth length, cm	mean (sd)
	median
	Q1, Q3
	range
	Missing
Head circumference, cm	mean (sd)
	median
	Q1, Q3
	range
	Missing
Apgar 1 score, n (%)	
≤3	
4-6	
≥7	
Missing	
Apgar 5 score, n (%)	
≤3	
4-6	
≥7	
Missing	

## Appendix A: Table shells

Table 9. Incidence of primary and secondary endpoints among pregnant women vaccinated with Boostrix before the 27th week of gestation

	Exposed			Incidence per 1000 persons or person-years (95% CI)
	Number of Persons	Number of Person years	Number of events	
Primary endpoints				
Pre-eclampsia and eclampsia a				N/A*
Intra-uterine infections a				N/A
Small for gestational age b				N/A*
Preterm delivery c				N/A
Secondary endpoints				
Poor fetal growth, IUGR a				N/A
Placental abruption a				N/A
Preterm pre-labor rupture of membranes (PPROM) d				N/A
Maternal death a				N/A
Stillbirth/fetal death e				N/A
With congenital anomalies				N/A
Spontaneous abortion e				N/A
With congenital anomalies				N/A
Therapeutic abortion e				N/A
With congenital anomalies				N/A
Post-partum hemorrhage f				N/A
Neonatal death g				N/A
Congenital anomalies at birth and through 6 months of age f				N/A
Congenital anomalies of nervous system				N/A
Congenital anomalies of eye				N/A
Congenital anomalies of ear, face, or neck				N/A
Congenital anomalies of cardiovascular system				N/A
Congenital anomalies of respiratory system				N/A
Clefts				N/A
Congenital anomalies of upper gastrointestinal system				N/A
Congenital anomalies of lower gastrointestinal system				N/A
Congenital anomalies of genital organs				N/A
Congenital anomalies of renal system				N/A
Congenital anomalies of musculoskeletal system				N/A
Congenital anomalies of limb				N/A
Congenital anomalies of integument				N/A
Other and unspecified congenital anomalies				N/A
Number of congenital anomalies (based on body system) per infant				N/A
0				N/A
1				N/A
2				N/A
3				N/A
≥4				N/A

a Identified among all pregnant women eligible for descriptive analysis

b Identified among KPSC live born infants, singleton only

c Identified among pregnant women with live birth, with index (vaccination) date prior to 37 weeks gestation

d Identified among pregnant women with index (vaccination) date prior to 37 weeks gestation

e Identified among pregnant women with pregnancy outcome

f Identified among pregnant women with KPSC delivery

g Identified among KPSC live born infants

h Wilson score interval with continuity correction

\* N/A=Not Applicable

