There were 19,554 (98.7%) pregnant women who received Tdap vaccination at or after 27 weeks of pregnancy (Table 4). There were 18,611 (94.0%) women who were vaccinated between 27 and 36 weeks gestation.

Table 4 Gestational age of women at Tdap vaccination during pregnancy at seven selected medical centers at Kaiser Permanente Southern California, 2016

Gestational age at vaccination	Frequency	Percent
<27 weeks	250	1.3%
27 weeks to 32 weeks	15,111	76.3%
33 weeks to 36 weeks	3,500	17.7%
>36 weeks	943	4.8%
TOTAL	19,804	100%

Note: Only those women meeting eligibility criteria, including membership, will be included in the analysis.

Rationale for historical comparison cohort

The estimated period of 1/1/2012-12/31/2013 was chosen for the unvaccinated comparison group because Tdap uptake ranged between 27% and 38% during this time (Table 5). The aim is to restrict the unvaccinated population to approximately 2012-2013 to minimize the concerns of confounding by indication. Given that Tdap uptake exceeded 65% starting in 2014, a concurrent unvaccinated cohort will yield a small and selective sample, and is not representative of an unvaccinated group.

Table 5 Tdap vaccine receipt during pregnancy at Kaiser Permanente Southern California, 2011-2016

Year	Tdap during pregnancy		No Tdap during pregnancy	
	Frequency	Percent	Frequency	Percent
2011	18325	40.0%	27471	60.0%
2012	13128	27.6%	34486	72.4%
2013	18309	38.3%	29519	61.7%
2014	32660	65.3%	17366	34.7%
2015	35754	68.4%	16513	31.6%
2016	38475	69.3%	17058	30.7%

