## Publication Record

Version	Date	Primary Author	Description
Draft 1.0	14 June 2019	PPD	1 st Draft for GSK Review
Final 1.0	26 July 2019	PPD	Final version incorporating GSK comments/edits
Final 2.0	02 December 2019	PPD	Final version of the SAP amendment following the protocol amendment (signed 25NOV2019)

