### **3. STUDY DESIGN**

#### **3.1 Overview of study design**

This is an observational retrospective matched cohort study. The study will be conducted among pregnant women who are members of KPSC.

The exposed cohort (from the 27th week of gestation) will consist of pregnant women who received the Tdap vaccine (Boostrix) on or after the 1st day of the 27th week of pregnancy during the vaccination period at ob-gyn clinics of seven selected medical centers. Approximately 15,000 women vaccinated with Boostrix will be included in this study over approximately a one-year period from January 2018 to January 2019.

The unexposed cohort will consist of women, pregnant sometime during the approximate estimated period from 1/1/2012 to 12/31/2013 who never received Tdap vaccine during pregnancy. The unexposed cohort of pregnant women will be matched 1:1 to the exposed cohort of pregnant women for comparisons of maternal and infant AEs between the two cohorts.

Subject-level data will be collected for pregnant women and their infants through the EHR. For each individual pregnant woman, analytical follow up will begin on the date they receive the Boostrix vaccine, or the index date for the unvaccinated cohort, and will end on the date of

disenrollment or the end of pregnancy, whichever came first. For the maternal death endpoint, pregnant women will be followed for 42 days after the end of pregnancy. Infants born in KPSC hospitals will be followed for 6 months.

In addition, women vaccinated with Boostrix before the 27th week of gestation, with membership at the date of vaccination, and who were not vaccinated with any other Tdap vaccine at any other time during the pregnancy will be included for a descriptive analysis (single arm).

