##### *Study population for descriptive analysis (secondary objective #2)*

- Pregnant women received prenatal care at KPSC
- Vaccinated with Boostrix before the 27th week of gestation and were not vaccinated with any other Tdap vaccine at any other time during the pregnancy
- Membership at the index (vaccination) date

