##### 4.2 Analyses of primary endpoints

We will calculate crude incidence and 95% CI for each primary endpoint for the exposed and unexposed cohorts. Unadjusted and adjusted RR with two-sided 98.75% CI will be estimated comparing the exposed cohort to the unexposed cohort, accounting for multiple comparisons.

Analysis of primary endpoints will be used to evaluate the safety of Boostrix vaccination and concluded to be non-inferior if the upper limit of the 98.75% CI for the adjusted relative risk is below 2.

Analyses of preeclampsia and/or eclampsia and intra-uterine infection will be performed on all pregnant women eligible for main analysis. For events identified any time after the index date (e.g., preeclampsia and/or eclampsia and intra-uterine infection), the incidence will consist of the total number of women with the condition in the numerator and the total person time in the denominator. The person-year for a pregnant woman will be the time from the index date to the date of each adverse event, end of the pregnancy, or disenrollment, whichever comes first. The unadjusted and adjusted relative risk with 98.75% CI will be estimated by Poisson regression models accounting for the follow-up time without and with adjustment for potential confounders. If the outcome is common (i.e., incidence > 2%), a Poisson regression model with a robust error variance will be used to estimate the relative risk (6). The robust Poisson regression will be performed using the SAS Proc GENMOD procedure with the REPEATED statement subject= Patient\_ID.

Analysis of SGA will be performed on live singleton infants born in KPSC hospitals, while analysis of preterm delivery will be performed on pregnant women with live births, and with an index date prior to 37 weeks gestation. For events identified at delivery (e.g., SGA and preterm delivery), the incidence will consist of the total number of women or infants with the condition in the numerator and the number of women or infants for whom the condition can be assessed in the denominator. The unadjusted and adjusted relative risk with 98.75% CI will be estimated by Poisson regression models with robust error variances without and with adjustment for potential confounders. The planned methods of analysis by primary endpoint are outlined in Table 4. See Appendix A, Table Shell 4 for details.

Table 4. Analytic population and statistical methods by primary endpoint

Primary endpoints	Analytic population	Statistical Methods

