For poor fetal growth, placental abruption, PPROM, and maternal death, the incidence will consist of the total number of women with the condition in the numerator and the total person time in the denominator. For poor fetal growth, placental abruption, and PPROM, the person-time for a pregnant woman will be the time from the index date to the date of each adverse event, end of the pregnancy, or disenrollment, whichever comes first. For maternal death, the person-time for a pregnant woman will be the time from the index date to the date of death, 42 days after delivery, or disenrollment, whichever comes first. The unadjusted and adjusted relative risk with 95% CI will be estimated by Poisson regression models, or Poisson regression models with robust error variances if incidence >2%, accounting for the follow-up time without and with adjustment for potential confounders.

For stillbirth/fetal death and transfusion during delivery hospitalization, the incidence will consist of the total number of women with the condition in the numerator and the number of women for whom the condition can be assessed in the denominator. The unadjusted and adjusted relative risk with 95% CI will be estimated by Poisson regression models, without and with adjustment for potential confounders.

Neonatal death and congenital anomalies will be identified among infants born in KPSC hospitals. The incidence of neonatal death will be calculated as the number of neonatal deaths in the numerator and the total number of infants born in KPSC hospitals in the denominator. The prevalence of congenital anomalies (overall, by type) will be calculated as the number of infants with a congenital anomaly in the numerator and the total number of infants born in KPSC hospitals in the denominator. The proportion of live births without congenital anomalies will be calculated as 1 minus the proportion of live births with congenital anomalies among all KPSC live born infants. The unadjusted and adjusted relative risk with 95% CI will be estimated by Poisson regression models, or Poisson regression models with robust error variances if incidence >2%, without and with adjustment for potential confounders.

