#### **4.4 Analysis of pregnant women vaccinated before the 27th week of gestation**

The analysis of pregnant women vaccinated with Boostrix before the 27th week of gestation will be descriptive. Due to the expected extremely small sample size, no formal hypothesis testing is planned.

The size of the study population and subgroups will be described. See Appendix A, Table Shell 6 for details. Baseline characteristics of pregnant women and their KPSC live born infants will be described. Continuous variables will be summarized by mean, median, Q1, Q3, range, and standard deviation; categorical variables will be summarized by frequency and percentage. See Appendix A, Table Shell 7 and Table Shell 8 for details.

The number of events for each primary and secondary endpoint in Table 1 among pregnant women vaccinated with Boostrix before the 27th week of gestation will be reported. The incidence will be calculated as the total number of women with the condition in the numerator and the number of women (or total person time) for whom the condition can be assessed in the denominator. Since we will likely observe no events or few events for most of the endpoints, the 95% Wilson score interval with continuity correction will be provided ([7](#)). See Appendix A, Table Shell 9 for details.

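### Person-year rates in Table Shell 9 depend on how early a woman was vaccinated; report events per 1000 women for the group vaccinated before week 27

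*SAP*

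**What the plan says.** The SAP file holds two versions. The one in force is Final 2.0, logged as "Final version of the SAP amendment following the protocol amendment (signed 25NOV2019"; everything here refers to it.

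- **Group.** SAP 3.2.1 defines the descriptive population as "Vaccinated with Boostrix before the 27th week of gestation", with membership required only at the vaccination date. No earliest gestational week is set.
- **Denominator.** SAP 4.4 gives incidence in this group over "the number of women (or total person time) for whom the condition can be assessed in the denominator". Shell 9 has columns for persons, person-years and events, and the incidence column is headed "Incidence per 1000 persons or person-years (95% CI". Shells 4 and 5 use the same heading for the main cohorts.
- **Clock.** By SAP 3.1, "analytical follow up will begin on the date they receive the Boostrix vaccine, or the index date for the unvaccinated cohort". For preeclampsia/eclampsia and intra-uterine infection, SAP 4.2 counts "the time from the index date to the date of each adverse event, end of the pregnancy, or disenrollment, whichever comes first". SAP 4.3 applies the same rule to poor fetal growth, placental abruption and PPROM. For maternal death it counts "the time from the index date to the date of death, 42 days after delivery, or disenrollment, whichever comes first". SAP 4.4 sets no different start for the early group.
- **Interval.** SAP 4.4 names a Wilson score interval with continuity correction. The source it cites is, by its title, about intervals for a single proportion.
- **Status.** SAP 3.1 and 4.4 describe a single-arm descriptive analysis in a very small group, with no hypothesis test.

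**The concern.** Secondary objective 2 is to describe how often these events occur after vaccination before week 27. In the main cohort the clock starts at week 27 or later, so follow-up to delivery lasts roughly 7 to 10 weeks. In the early group it starts at vaccination and can run for much longer. Where an endpoint is concentrated late in pregnancy, the extra early weeks enlarge the denominator and add little to the numerator. The rate then reflects the week of vaccination as well as the woman's risk.

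Two things follow. Within Shell 9, a person-year rate describes risk in a pregnancy poorly, because it averages over whatever mix of vaccination weeks happens to occur. Across tables, the shared heading and units invite a reader to set Shell 9 beside Shells 4 and 5, and neither SAP 4.4 nor the shell warns against it. Shell 7 adds to the difficulty: for this same early group it bands gestational age at index as 27-30, 31-36 and 37 or more weeks, where no eligible woman can fall. The baseline table would therefore not show how early these women were vaccinated.

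**Working it through.** The documents give no figure to reproduce: no rate ratio, no gestational age at delivery, and no distribution of vaccination week below 27. What follows is illustration under stated assumptions.

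**Formula.** With few events and equal risk per pregnancy, rate ≈ risk / mean person-time. The factor by which the early-group rate is lower is

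F = (delivery week − early index week) / (delivery week − mean main-cohort index week).

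**Main-cohort index week.** The counts come from protocol Table 4 (2016 data): 15,111 women in the band "27 weeks to 32 weeks", 3,500 at 33 to 36 weeks and 943 above 36 weeks, 19,554 in all. The typical week inside each band is assumed.

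- Typical weeks 30, 35, 38: (15,111×30 + 3,500×35 + 943×38)/19,554 = 31.28 weeks.
- Typical weeks 28, 35, 38: (15,111×28 + 3,500×35 + 943×38)/19,554 = 29.74 weeks.

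**One worked case.** Assume delivery at week 39.3 and mean index 31.28, so main-cohort follow-up is 39.3 − 31.28 = 8.02 weeks. Take a risk of 5.8%, the midpoint of the 5.5% and 6.1% for chorioamnionitis cited in protocol 1.1. Rate per 1000 person-years = 1000 × 0.058 / (weeks × 7/365.25).

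| Index week | Follow-up (weeks) | Rate per 1000 person-years | F |
|---|---|---|---|
| 31.28 (main cohort) | 8.02 | 377 | 1.00 |
| 26 | 13.3 | 228 | 1.66 |
| 20 | 19.3 | 157 | 2.41 |
| 12 | 27.3 | 111 | 3.40 |
| 8 | 31.3 | 97 | 3.90 |

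The risk is 5.8% in every row.

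**Sensitivity.** Let delivery run from 38.5 to 40 weeks and mean main-cohort index from 29.74 to 31.28. Main-cohort follow-up is then between 38.5 − 31.28 = 7.22 and 40 − 29.74 = 10.26 weeks.

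| Early index | F, lowest | F, highest |
|---|---|---|
| week 4 | 36/10.26 = 3.51 | 34.5/7.22 = 4.78 |
| week 20 | 20/10.26 = 1.95 | 18.5/7.22 = 2.56 |
| week 24 | 16/10.26 = 1.56 | 14.5/7.22 = 2.01 |
| week 26 | 14/10.26 = 1.36 | 12.5/7.22 = 1.73 |
| 26 weeks 6 days (26.86) | 13.14/10.26 = 1.28 | 11.64/7.22 = 1.61 |

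Overall, F is about 1.3 to 4.8.

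**Maternal death.** The 42 days add 6 weeks to both follow-up times. With delivery at week 39 and main index at week 30, F = (39 − e + 6)/15, where e is the early index week: 41/15 = 2.73 at week 4, 21/15 = 1.40 at week 24 and 18.14/15 = 1.21 at 26 weeks 6 days. Without the 42 days the same inputs give 3.89, 1.67 and 1.35.

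**Events before week 27.** If the early group has a fraction x more events because it is observed for longer, F is divided by (1 + x). With x = 0.10, for example, 2.41 becomes 2.19.

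**Per-woman denominator.** Equal risk per pregnancy gives a ratio of 1.0 whatever the index week. Persons and events are already columns in Shell 9.

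**The case against.** The strongest reply is that nothing in the plan compares these tables. The group is single-arm and tiny: 250 of 19,804 women in 2016, which scales to about 15,000 × 250/19,554 = 192 women. Persons and events stand beside the rate, so anyone can work out the risk. With 10 events, an exact 95% Poisson interval runs from 0.48 to 1.84 times the estimate, so a factor near the low end would be lost in sampling error. This largely stands. It limits the consequence, but it does not make the person-year rate a good description of incidence, and factors above about 2 exceed that noise.

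Second, SAP 4.4 offers women or person-time, and the Wilson interval suits a proportion. The text is therefore ambiguous and does not fix a person-year metric for each endpoint. This also stands. The N/A marks in Shell 9, as read from the PDF, cannot be tied reliably to columns, so they do not settle it. The case rests on SAP 4.4, the headings and the person-time rules in 4.2 and 4.3.

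Third, person-time deals with censoring, which matters more here because membership is required only at vaccination. This is a real cost of the per-woman measure and is addressed in the fix.

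A reader might go further and infer that the report will show early vaccination as safer, that every person-time endpoint will look much rarer, or that these events hardly occur before week 27. The documents support none of these. No cross-table safety conclusion is planned, women vaccinated near week 26 give a modest factor, and the documents give no timing of events before week 27.

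**Conclusion.** The point holds as a reporting weakness. Where Shell 9 uses person-years from vaccination, the rate for a late-pregnancy endpoint falls as vaccination gets earlier at unchanged risk per pregnancy, and it falls below the rates in Shells 4 and 5.

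The factor of about 1.3 to 4.8 is an illustration and not a bound. It rests on assumed vaccination weeks (4 to 26 weeks 6 days), assumed delivery weeks (38.5 to 40), assumed typical weeks within the protocol Table 4 bands, and equal risk per pregnancy. A narrower span, such as the 1.7 to 3.9 in the worked case, reflects one choice of weeks and should not be read as a finding. Maternal death is less affected, and events before week 27 would shrink the factor.

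No primary endpoint, relative risk or comparative conclusion is touched. The change is worth making because it is cheap and because it brings the measure into line with the interval already named.

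**What to change.** In SAP 4.4 and Shell 9:

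1. Report each maternal endpoint as events per 1000 women assessed, with the Wilson interval already named.
2. Add the number of women who disenrolled before the end of pregnancy. Their follow-up is incomplete, and the lost-to-follow-up row does not cover them: SAP 5.1 uses that term for women with continuous membership whose pregnancy end date stays missing.
3. If person-year rates are kept as a supplement, give them a Poisson-based interval and footnote that they are not comparable with Shells 4 and 5.

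Starting person-time at week 27 is not a substitute. It drops events between vaccination and week 27, which objective 2 should describe. It also leaves a gap: (39.3 − 27)/8.02 = 12.3/8.02, about 1.5-fold, in the worked case.

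The cost is a few lines of SAP text and one table program, with no new data. There are two drawbacks. Women who disenroll count fully in the denominator, which is why their number must be shown. The units will also differ from the person-year rows of Shells 4 and 5, although those shells already show persons and events. The gestational-age bands in Shell 7 can be corrected in the same edit.
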